5.5 Study Activities

- All qualified patients will be treated with AZD7442 600 mg IM or IV at baseline.
- All qualified patients will complete a baseline Patient Experience/Clinical Outcome Assessment (COA) survey (Day 1) prior to treatment with AZD7442 600 mg IM or IV.
- All qualified patients will complete follow-up Patient Experience/COA surveys on days 2, 30, 60, 90, 120, 150, 180, 181, 210, 240, 270, 300, 330 and 360 post-baseline.

- All qualified patients will complete QoL assessment on days 2, 30, 90, 180, 270, and 360 post-baseline.
- All qualified patients will have serum concentration of AZD7442 obtained at days 30, 90, 180, 270 and 360 post-baseline.
- All qualified patients will have SARS-Cov-2 RBD-IgG antibody level obtained at baseline, days 90, 180, 270 and 360 post-baseline
- At Day 30 post-baseline, all patients will have blood obtained for T-cell assay. Measurements of CD4 T-cell and CD8 T-cell function will be performed.
- Blood will be obtained for repeat T-cell assay (CD4/CD8) at Day 210 post-baseline in a selected subset of 120 hematologic malignancy and 60 solid tumor patients.
- Repeat T-cell functional testing, SARS-CoV-2 RBD-IgG and serum concentration of AZD7442 will be performed in patients who become SARS-CoV-2 RNA by RT-PCR positive at approximately 10 days or according to study site guidelines after the patient develops a positive test.

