9.3 Follow-Up Activities

Follow-Up activities are as follows:

- At Day 180 post-baseline, all patients will be administered a repeat dose of AZD7442 600 mg IM or IV. The window for this treatment will be +/- 5 days from the actual due date. The dose will be administered in the same manner as the baseline dose unless patient circumstances require a different route of administration. All requirements listed above for baseline AZD7442 administration both IV and IM will be followed for the repeat dose including the one-hour post-dose observation period.
- Patients will complete follow-up Patient Experience/COA surveys on days 2, 30, 60, 90, 120, 150, 180, 181, 210, 240, 270, 300, 330 and 360 post-baseline at home. The window for these surveys will be +/- 5 days from the actual survey due date except for day 2 survey which is +5 days only.
*NB - Study participants will complete all surveys via mobile phone, desktop, laptop, tablet computer or via Call Center. The study site is not responsible for patient completion of the surveys.
- Patients will complete QoL assessments on days 2, 30, 90, 180, 270, and 360 post-baseline at home. The window for these assessments will be +/- 5 days from the actual due date except for day 2 assessment which is + 5 days only.
- Site personnel will obtain blood for serum concentration of AZD7442 at days 30, 90, 180, 270 and 360 post-baseline in the office for all patients. The window for these blood draws will be +/- 5 days from the actual due date. All

serum concentration measurements will be sent to PPD Bioanalytical Laboratory in Richmond, VA for analysis.

- Site personnel will obtain blood for RBD-IgG antibody level at days 90, 180, 270 and 360 post-baseline in the office for all patients. The window for these blood draws will be +/- 5 days from the actual due date. All RBD-IgG antibody levels will be sent to LabCorp for analysis.
- Site personnel will obtain blood for T-cell assay at Day 30 post-baseline in the office for all patients and send to Isoplexis in Branford, CT for analysis. A subset of patients will be selected including 120 patients with hematologic malignancy and 60 patients with solid tumors in order to have site personnel obtain blood for repeat T-cell assay at Day 210 post-baseline in the office and send to Isoplexis in Branford, CT for analysis. The window for these blood draws will be +/- 5 days from the actual due date.

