13.2 Primary Endpoint Assessment

AZD7442 serum concentrations at 30, 90, 180, 270 and 360-days post-baseline will be assessed using a mixed model for repeated measures. The primary endpoint will be analyzed for the Intent-To-Treat (ITT) and Per-Protocol (PP) populations.

**14.0
Secondary
And Exploratory
Endpoints:
Overall Study**

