14.2 Secondary Endpoint Analysis

All secondary endpoints will be analyzed for the Intent-To-Treat (ITT) population with a Per-Protocol (PP) sensitivity analysis.

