
17.0 Statistical Considerations
	
17.1 Sample Size Estimation
 
This program will recruit approximately 1,500 treated cancer patients divided into approximately 1,200 qualified solid tumor and 300 qualified hematologic malignancy patients from approximately 75 hematology/oncology medical practice locations throughout the United States. It is expected that on average, each site will enroll 16 solid tumor and 4 hematologic malignancy patients.
 
17.2 Sample Size Power
 
With a sample size of 1500 patients, the power to detect a non-inferiority margin of 5 mcg/ml with a standard deviation of 25 mcg/ml and Type I error rate of 1% is estimated to be approximately 80% when comparing the serum concentration levels between solid tumor and hematologic malignancy groups. The assumed comparison is between 1200 solid tumor and 300 hematologic malignancy patients. A target sample of 1500 patients will provide adequate size to analyze all of the secondary endpoints identified in the baseline and follow-up patient experience/COA surveys and the QoL surveys.
 
At the time of interim analysis, the power to detect a 5 mcg/ml non-inferiority margin with a standard deviation of 25 mcg/ml and Type I error rate of 1% is estimated to be approximately 45%. This assumes a sample of 600 solid tumor and 150 hematologic malignancy patients.
 
17.3 Stratification
 
This is an open-label, pragmatic, multi-center study of participants receiving AZD7442 600 mg IM or IV for prevention of symptomatic SARS-CoV-2 infection including SARS-CoV-2 related hospitalization and/or SARS-CoV-2 related death.

Patients will be stratified based on type of cancer (solid tumor vs hematologic malignancy) with additional stratification for concomitant treatment regimen of chemotherapy only, immunotherapy only, targeted therapy only and other therapy/combination therapy. It is assumed that 80% of enrolled cancer patients will have solid tumors. Patients will be sub-stratified by: currently on active treatment, ≤ 3 months post-treatment or > 3 months and ≤ 12 months post-treatment.

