17.4 Populations for Analysis

The study will analyze two populations as defined by Intent-To-Treat (ITT) and Per Protocol (PP) criteria.

- The ITT population includes all participants who complete enrollment, complete the baseline Patient Experience/COA survey, baseline QoL assessment, baseline SARS-CoV-2 RBD-IgG, undergo AZD7442 600 mg IM or IV administration, complete at least one serum concentration AZD7442 measurement post-baseline AZD7442 administration, one RBD-IgG post-baseline, complete the Day 30 T-Cell assay, complete at least one follow-up Patient Experience/COA survey and one QoL assessment.
- The PP population includes all participants who complete all AZD7442 600 mg IM or IV administrations, complete the baseline Patient Experience/COA surveys, complete the baseline QoL assessment, complete the baseline SARS-CoV-2 RBD-IgG antibody level, complete the Day 30 and Day 210 T-Cell assay, complete 75% of follow-up Patient Experience/COA surveys, 75% of QoL assessments, 75% of RBD-IgG antibody levels and 75% of serum concentration of AZD7442 measurements post-baseline AZD7442 administration.

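### The Per-Protocol definition requires a Day 210 T-cell assay that the sampling sections schedule for only 180 selected patients, which caps that analysis set at 12% of the trial

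*Protocol*

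**What the plan says.** Section 17.4 defines two analysis populations. PP membership requires, without any exemption, that a participant "complete the Day 30 and Day 210 T-Cell assay, complete 75% of follow-up Patient Experience/COA surveys". The 75% tolerance applies to surveys, QoL assessments, RBD-IgG levels and concentration samples. It does not apply to the T-cell assays.

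Two sections say who is actually drawn at Day 210. Section 5.5 places the repeat assay "at Day 210 post-baseline in a selected subset of 120 hematologic malignancy and 60 solid tumor patients". Section 9.3 agrees: "A subset of patients will be selected including 120 patients with hematologic malignancy and 60 patients with solid tumors". Section 17.1 gives the planned total as "approximately 1,200 qualified solid tumor and 300 qualified hematologic malignancy patients".

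Other text reads differently:
- Section 5.6 lists at least two CD4/CD8 measurements among the data for all treated participants.
- Section 1.1 describes patients willing to be drawn twice for T-cell assays.
- Section 8.1 requires willingness for draws at Days 30 and 210.
- Section 8.2 excludes patients unwilling to be drawn twice.
- The Schedule of Activities marks the assay at Day 210 with no note about a subset.

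PP is not a side analysis. Section 13.2 states: "The primary endpoint will be analyzed for the Intent-To-Treat (ITT) and Per-Protocol (PP) populations". Section 14.2 states: "All secondary endpoints will be analyzed for the Intent-To-Treat (ITT) population with a Per-Protocol (PP) sensitivity analysis". Sections 17.6 and 17.9 repeat these roles.

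**The concern.** A PP set is meant to hold patients who followed the protocol. Under 17.4 as written, a patient who receives both doses and gives every sample scheduled for them still fails PP if they were not selected for the Day 210 draw. They fail for lacking a test that 5.5 and 9.3 never asked them to have.

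The ITT and PP results for serum concentration would then differ mainly because of sub-study selection. Disagreement between them would be hard to interpret, and agreement would say little about adherence. Pooled PP summaries labelled as all patients would describe a different population from the one enrolled.

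The criterion also does little for the endpoints. None of those listed in 14.1, 14.3 or 16.1 names the Day 210 assay, and 17.8 names only two T-cell timepoints: Day 30 and confirmed infection.

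**Working it through.** **Inputs.** Planned sample: 1,200 solid and 300 hematologic (17.1). Day 210 subset: 60 solid and 120 hematologic (5.5, 9.3). Margin 5 mcg/ml, SD 25 mcg/ml, Type I error 1% (17.2, sidedness not given there). Section 17.6 uses a two-sided 0.01 level for the primary endpoint.

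**Step 1: ceiling on PP.**
- All patients: (120 + 60) / 1,500 = 180 / 1,500 = 12%.
- Hematologic: 120 / 300 = 40%.
- Solid: 60 / 1,200 = 5%.
- Excluded whatever their adherence: 300 − 120 = 180 hematologic and 1,200 − 60 = 1,140 solid, together 1,320 of 1,500 (88%).

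This is an upper bound, because the dosing, baseline and 75% rules can only shrink the set further. T-cell testing after a positive RT-PCR is triggered by infection and is not a Day 210 assay, so it does not lift the ceiling.

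**Step 2: case mix.** Planned solid:hematologic = 1,200:300 = 80:20. At the PP ceiling it is 60:120 = 33:67.

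**Step 3: reproduce the plan's power figures.** Two-sample normal approximation: SE = 25 × √(1/n₁ + 1/n₂); power = Φ(5/SE − z), with z = 2.326 (one-sided 1%) or 2.576 (two-sided 1%).
- Full sample: SE = 25 × √(1/1,200 + 1/300) = 1.61; 5/SE = 3.098. Power is Φ(0.772) = 78.0% one-sided and 69.9% two-sided. Section 17.2 says approximately 80%.
- Interim, 600 and 150: SE = 2.28. Power is 44.6% one-sided and 35.0% two-sided. Section 17.2 says approximately 45%.

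The one-sided figures match the plan's, allowing for its word approximately.

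**Step 4: the same calculation at the PP ceiling, as illustration.**
- SE = 25 × √(1/60 + 1/120) = 3.95; 5/SE = 1.265.
- One-sided: Φ(1.265 − 2.326) = Φ(−1.061) = 14.4%.
- Two-sided: Φ(1.265 − 2.576) = Φ(−1.311) = 9.5%.
- 99% confidence interval half-width: 2.576 × 3.95 = 10.2 mcg/ml, against 2.576 × 1.61 = 4.2 in the full sample. The PP half-width is about twice the 5 mcg/ml margin.

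**Step 5: after the fix.** If the assay is no longer required of unselected patients, the PP ceiling returns to 1,500 (1,200 and 300).

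**The case against.** The strongest reply is that 17.4 agrees with 5.6 and the Schedule of Activities, and sits easily with 1.1, 8.1 and 8.2. If every patient was meant to have the Day 210 assay, 17.4 is right, 5.5 and 9.3 are wrong, and the ceiling disappears. This stands in part: the root defect is an unresolved conflict over who has the assay, so a flat claim that only 180 patients will ever have it goes further than the document. The subset reading is still the better one. Sections 5.5 and 9.3 assign the draw explicitly and give the same numbers, whereas 1.1, 8.1 and 8.2 concern willingness, which fits later selection of a subset.

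A reader might also draw stronger conclusions that the protocol does not support:
- **That the subset is hand-picked.** The protocol says selected and gives no method. Selection could be random within disease type, and the method may be set out in an analysis plan not seen here.
- **That PP is a failed powered analysis.** The protocol claims no power for PP. The solid versus hematologic comparison is listed as secondary in 3.2 and 14.1. Section 17.6 analyses log-adjusted concentrations in a mixed model, so the raw-scale figures in step 4 only illustrate the loss of precision.
- **That the altered mix biases the disease contrast.** The 17.6 model includes disease category, so the mix alone does not bias that contrast. It affects pooled summaries.
- **That the main result is undermined.** ITT requires the Day 30 assay but not the Day 210 assay.

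An analysis plan could refine the definition, but the protocol already states a rule that conflicts with its own sampling scheme.

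**Conclusion.** The point holds as a contradiction between the PP definition in 17.4 and the sampling in 5.5 and 9.3. On the explicit sampling text, PP is limited to at most 180 of 1,500 patients, with hematologic patients in the majority and membership driven by sub-study selection. It would be a very imprecise check on the primary endpoint rather than no check at all, and the same weakness carries over to the PP sensitivity analyses of the secondary endpoints.

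The 12% ceiling assumes that the subset reading is the intended one and that enrollment meets its targets. The 33:67 mix further assumes that both parts of the subset fully meet the other PP rules. If universal Day 210 testing was intended, the ceiling is 1,500 and the error lies in 5.5 and 9.3. Either way the text needs correction before analysis.

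**What to change.** In 17.4, remove the Day 210 T-cell assay from the general PP definition. Alternatively, require it only of patients selected for the Day 210 draw, or only for PP analyses of the T-cell sub-study. Leave the dosing, baseline, Day 30, survey, QoL, RBD-IgG and concentration rules as they are, since nothing here shows them to be wrong.

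Then reconcile 1.1, 5.6, 8.1, 8.2 and the Schedule of Activities with 5.5 and 9.3, so that the protocol says once and consistently who has the Day 210 assay.

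If the subset is intended, the cost is one line in 17.4 plus matching text edits, with no operational change. If universal testing was intended, 5.5 and 9.3 must change instead, and that adds up to 1,500 − 180 = 1,320 Day 210 assays to the schedule they now describe.

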17.5 Missing Data

There are several potential missing data considerations within this study. These are outlined as follows with associated methods of handling the missing information.

- Serum AZD7442 concentration: For both the ITT and PP populations, if a patient has serum AZD7442 at Day 30 and Day 90 but does not have an additional timepoint at Day 180 then the value for the missing serum AZD7442 concentration data point at Day 180 will be predicted from the linear regression of the log

AZD7442 serum concentration from the Day 90 analysis. Otherwise, the missing AZD7442 serum concentration data will be treated as missing data.

- SARS-CoV-2 infection: Will be determined through the documentation of SARS-CoV-2 diagnosis either through SARS-CoV-2 by Rt-PCR test, the medical record or claims information. Multiple locations of documentation will be considered a confirmed diagnosis.

- Clinical Outcome Assessment/Quality of Life Assessment: If data are missing through the survey collection process, then only the relevant measures will be calculated. Appropriate consideration of missing values will be addressed for time points comparison either through the non-inclusion of the patient outcome in that time point and/or within regression model assessment.

- RBG-IgG antibody level: Correlations will be determined where there is complete information only.

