13.1 Primary Endpoint

The study's primary endpoint will assess AZD7442 serum concentration collected on days 30, 90, 180, 270, and 360 post-baseline in all patients.

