
15.0 Interim Analysis
	
the analysis will determine which group is more likely to experience such infections.
 
An interim analysis will be performed after the first 6-month assessments are completed for the first 50% of the targeted patient sample for each malignancy, i.e., 750 patients including 600 solid tumor and 150 hematologic malignancies. The primary endpoint of the interim analysis will be the serum concentration of AZD7442 for all patients with comparisons between disease categories.
 
Secondary analyses will be conducted on the following measures in all patients included in the interim analysis set:
 
 • Incidence of break-through infections in all patients and then sub-divided into solid tumor and hematologic malignancy. • Time to infection compared between solid tumor and hematologic malignancy • RBD-IgG levels for all patients with comparisons between disease category • CD4/CD8 levels for all patients with comparisons between disease category

16.0 Immunological Sub-Study Endpoints
	
16.1 Immunologic Sub-Study Endpoints
 
 • Comparison of CD4 T-cell and CD8 T-cell function in all cancer patients at 30 days post initial administration of AZD7442 to similar tests performed in normal healthy donor subjects • Comparison of the relationship between different cancer treatment regimens and T-cell function in all cancer patients at 30 days post administration of AZD7442 • Comparison of the relationship between type of cancer (solid vs. hematologic) and T-cell function in all patients at 30 days post administration of AZD7442 • Comparison of the immunologic profile relating to AZD7442 serum level and T-cell function at the time of PCR positive SARS-CoV-2 infection in all cancer patients to Day 30 T-cell functionality • Comparison of the relationship between change from Day 30 in AZD7442 serum level, T- cell function and World Health Organization Ordinal Scale

	
(WOS) for SARS-CoV-2 disease severity in all cancer patients with documented PCR positive SARS-CoV-2 infection
 
 • Comparison of the relationship between change from Day 30 in AZD7442 serum level, T- cell function and World Health Organization Ordinal Scale (WOS) for SARS-CoV-2 disease severity in all cancer patients with documented RT-PCR positive SARS-CoV-2 infection based on type of cancer treatment.

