17.6 Evaluations of Primary and Secondary Endpoints

The primary and secondary endpoints will be evaluated for the intent-to-treat and per protocol patient populations. The primary comparisons will be the serum concentration of AZD7442 at Days 30, 90, 180, 270 and 360 post-baseline. Serum concentration comparisons of the log-adjusted serum AZD7442 concentration will be analyzed using linear mixed models for repeated measures. Models will include disease category, overall dose, and dose/kg accounting for concomitant treatment regimen category along with appropriate treatment and time interactions. An unstructured covariance matrix will be assumed, however, in the event of non-convergence, compound symmetry, and AR (1), covariance structures will be attempted, in that order. The Least Square Means Differences, and their 95% CIs, will be reported for each timepoint (e.g., Days 30, 90, 180, 270, and 360 post-treatment).

Additional comparisons for Quality of Life (QoL) will be made between the disease category cohorts and concomitant treatment regimen categories. The disease category cohorts are solid tumor cancers and hematologic cancers. Concomitant treatment regimen categories will be defined as chemotherapy only, immunotherapy

only, targeted therapy only, other therapy/ combination therapy only. Differences in the primary endpoints will be assessed using a two-sided statistical significance level of 0.01, adjusting for planned multiple comparisons. All other differences will be assessed using a two-sided statistical significance level of 0.05.

The secondary endpoint comparisons will be made:

- between concomitant treatment regimen categories and
- between disease category cohorts

The between concomitant treatment regimen categories will account for the between disease category analyses. These secondary endpoint comparisons will be made using a logistic regression or linear mixed model accounting for potential patient and disease factors where appropriate. Additional secondary endpoints are as noted previously. The secondary endpoints will be analyzed for the Intent-To-Treat (ITT) population with a Per-Protocol (PP) sensitivity analysis.

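### Day 180 serum concentration is at risk: its draw is not ordered against the Day 180 redose, and missing values get one unneeded, undefined regression prediction

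*Protocol*

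**What the plan says.** **Timing.** Protocol 9.3 states: "At Day 180 post-baseline, all patients will be administered a repeat dose of AZD7442 600 mg IM or IV". For the dose: "The window for this treatment will be +/- 5 days from the actual due date". In a separate item, "Site personnel will obtain blood for serum concentration of AZD7442 at days 30, 90, 180, 270 and 360 post-baseline", and for that draw: "The window for these blood draws will be +/- 5 days from the actual due date". The Schedule of Activities marks both under Day 180. No section says that the draw precedes the dose or ties it to the actual dose date.

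**Missing values.** Protocol 17.5 applies to the ITT and PP populations. If Day 30 and Day 90 are present and Day 180 is absent, "the value for the missing serum AZD7442 concentration data point at Day 180 will be predicted from the linear regression of the log" concentration, with a reference to the Day 90 analysis. All other missing concentrations stay missing.

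**Where the value is used.** The primary endpoint (13.1) is "AZD7442 serum concentration collected on days 30, 90, 180, 270, and 360 post-baseline in all patients". On the analysis, 17.6 says: "Serum concentration comparisons of the log-adjusted serum AZD7442 concentration will be analyzed using linear mixed models for repeated measures". The interim analysis (15.1) follows the 6-month assessments of the first 750 patients: "The primary endpoint of the interim analysis will be the serum concentration of AZD7442 for all patients with comparisons between disease categories". Day 180 is the last visit that feeds it.

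**The concern.** Day 180 is the only planned measurement at the end of the first dosing interval. If some samples are taken before the redose and others after it, the visit mean is no longer an end-of-interval level, and the spread contains a component that has nothing to do with patients. Without a required order and recorded times, this cannot be undone at analysis.

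The fill rule is a second, independent weakness at the same visit. A repeated-measures model already uses a patient's Day 30 and Day 90 values when Day 180 is missing. A predicted value placed in the data adds nothing, and it carries no residual error unless something further is done. 17.5 also leaves open whether the line is the patient's own or a population regression, and if the latter, whether it is fitted by disease group.

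The two interact. A line through a patient's own Day 30 and Day 90 values predicts a level without redosing, while an observed Day 180 value may be post-redose.

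**Working it through.** The plan gives no figure for either issue. The half-life, absorption rate, post-dose share, rise, missing share and correlation below are all assumptions.

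**1. Range of compliant timings.** Dose and draw may each fall on Day 175 to 185. Dose on 175 and draw on 185 gives 10 days after the redose; the reverse gives 10 days before it.

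**2. Post-dose to pre-dose ratio.** With first-order elimination, half-life T, equal doses 180 days apart and full absorption, the ratio is 1 + 2^(180/T):
- T = 60: 1 + 8 = 9.0
- T = 90: 1 + 4 = 5.0
- T = 120: 1 + 2.83 = 3.83

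For IM dosing, C(t) = ka/(ka − ke) × (e^(−ke·t) − e^(−ka·t)). Holding the residual of the first dose at its Day 180 level, the ratio s days after redosing is 1 + C(s)/C(180). With absorption half-life 3 to 10 days and s = 5 to 10, it runs from 1.75 (T = 120, absorption 10, s = 5) to 7.33 (T = 60, absorption 3, s = 10). Minutes after an IM dose, C(s) is near zero and the ratio is near 1.

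**3. Effect on the Day 180 mean.** On the log scale, a share p of post-dose samples multiplies the geometric mean by ratio^p. Over ratios 1.8 to 9, p = 5% gives +3% to +12%, and p = 10% gives +6% to +25%.

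**4. Effect on the group comparison.** Equal shares in both disease groups cancel in the log difference, so bias needs an imbalance. On the mcg/ml scale of 17.2 (margin 5, SD 25, 1,200 versus 300), a post-dose rise R needs an imbalance of 5/R to shift the difference by the whole margin: R = 50, 100 or 150 gives 10, 5 or 3.3 percentage points.

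Equal shares still add variance: SD = √(25² + p(1 − p)R²). With p = 10%, R = 50 gives √(625 + 225) = 29.2, and R = 150 gives √(625 + 2,025) = 51.5. As a base, 17.2 states about 80% power at Type I error 1%; a one-sided 1% test gives 78.0%. The two inflated SDs reduce that to 63% and 21%.

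**5. The fill, by reading of the regression** (single-visit comparison, values missing completely at random).

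*Fitted within disease group.* With missing share m, exchangeable correlation ρ and R² = 2ρ²/(1 + ρ), naive SE / true SE = √{[(1 − m) + mR²] / [(1 − R²)/(1 − m) + R²]}.
- m = 5%, ρ = 0.9 (R² = 0.853): √(0.993/1.008) = 0.99; nominal two-sided 0.01 becomes 0.011.
- m = 30%, ρ = 0.5 (R² = 0.333): √(0.800/1.286) = 0.79; nominal 0.01 becomes 0.042.

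*Pooled over disease groups.* In simulation (2,000 runs per setting, 10–30% missing), rejection at a true null stayed at 0.006 to 0.012 for nominal 0.01. But a 5 mcg/ml difference that appears only by Day 180 is estimated as 5(1 − m), which is 4.75 at 5% missing and 3.5 at 30%. With SE = 25√(1/300 + 1/1,200) = 1.614, the one-sided 1% non-inferiority error 1 − Φ(2.326 − 5m/1.614) becomes 1.5% to 8.1%.

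*The patient's own line.* Day 180 lies 90 days past Day 90 and the slope comes from 60 days, so the prediction is y90 + 1.5(y90 − y30) = 2.5·y90 − 1.5·y30. Its measurement-error variance is 2.5² + 1.5² = 8.5 times that of one value. In simulation (ρ = 0.5, 30% missing) the SD of the estimated difference was 0.092 and the mean estimated SE 0.094, in SD units. The SE is honest but well above the complete-data √(1/300 + 1/1,200) = 0.065.

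**The case against.** The protocol permits a mix of pre- and post-dose samples but does not produce one. Dose and draw share one visit column, and a 10-day gap needs two trips. Surveys at Days 180 and 181 parallel those at Days 1 and 2, where the first precedes dosing, which suggests a pre-dose Day 180. This makes frequent post-dose sampling less likely, so calling the Day 180 data corrupted would go too far. It does not supply an order. Elsewhere the protocol does fix one: the baseline survey comes before treatment (5.5). The baseline requirements that 9.3 carries over to the second dose concern administration, and baseline has no serum concentration draw.

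Four further inferences are tempting and not supported:
- *Confidence intervals are too narrow.* This follows only from a regression fitted within disease group. The pooled and own-patient readings do other harm.
- *The rule invents values for patients who died or withdrew.* The mixed model under missing-at-random also extrapolates implicitly for them, so this does not separate the rule from its replacement.
- *Post-dose samples are generally 3.8 to 9 times the trough.* That holds for a fully absorbed dose, such as IV, which 9.2 restricts to listed conditions.
- *Day 180 is the interim's main visit.* 15.1 does not say so; Days 30 and 90 are also available.

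The fill is also narrow: one of five visits, and only with both earlier values present. That it enters as observed data is an inference from the contrast with the other gaps, which stay missing. A SAP could add a variance correction, but the protocol itself fixes a single prediction.

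**Conclusion.** Both parts stand, as a risk to one primary-endpoint visit that also closes the interim data. They should be fixed, but they do not invalidate the primary analysis.

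On timing, compliant samples can span up to 10 days either side of the redose. The Day 180 level is then at risk of upward bias and extra variance; the solid-versus-hematologic difference is biased only if the post-dose share differs between groups. The size rests on an assumed half-life and absorption rate, and the share of post-dose samples cannot be known from the protocol.

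On the fill, the firm conclusion is that the rule is undefined and unnecessary. No single percentage describes its harm. The quantities in step 5 of the working each belong to one reading and to the missing shares and correlations assumed there.

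**What to change.** In 9.3, state that the Day 180 serum concentration sample, and the RBD-IgG sample that shares its window, is drawn before the second dose, and record the date and time of both draw and dose. State that any sample taken after the redose is left out of the Day 180 estimate or modeled by time since last dose.

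In 17.5, delete the Day 180 regression prediction and let the mixed model of 17.6 handle missing concentrations under missing-at-random.

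The cost is one instruction to sites and the removal of one rule, with no extra visit or sample and no change to dosing. A few out-of-order samples would drop out of the Day 180 mean.
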